5. STUDY TREATMENT

5.1. Study Drug

5.1.1. Description, Packaging, and Labeling

The description of the study drug is presented in [Table 2](#).

Table 2 Tapinarof Cream

Drug name:	DMVT-505 (tapinarof)
Physical description	White to off-white cream
Unit dose strength/how supplied	1% (10 mg/g)/30 gram, tube
Route of administration/duration	Topical/up to 40 weeks
Dosing instructions:	Once daily topical application of thin layer to all affected areas (see Section 5.1.5)
Manufacturer	GlaxoSmithKline

Study drug will be dispensed to subjects at the clinical site in appropriately labeled tubes. All labels for tapinarof cream, 1% to be distributed in the participating countries will meet all applicable requirements of those countries.

5.1.2. Storage

All study drug must be stored in a secure environmentally-controlled and monitored (manual or automated) area in accordance with the labelled storage conditions, with access limited to the Investigator and authorized site staff.

5.1.3. Handling and Disposal

Under normal conditions of handling and administration, study drug is not expected to pose significant safety risks to site staff. In the case of unintentional occupational exposure notify the monitor, Medical Monitor and/or the Sponsor study contact.

A Material Safety Data Sheet (MSDS)/equivalent document describing occupational hazards and recommended handling precautions either will be provided to the Investigator, where this is required by local laws, or is available upon request from the Sponsor.

Arrangements will be made for used and unused drug supplies to be returned to the Sponsor or Sponsor designee, or for destruction on site following acceptable, documented procedures.

Further guidance and information for final disposition of unused study drug will be provided.

5.1.4. Preparation

No special preparation of study drug is required.

5.1.5. Administration of Study Drug

5.1.5.1. Treatment by Physician Global Assessment Score

Subjects entering with a PGA ≥ 1 will receive treatment with tapinarof cream, 1% until they achieve a PGA score of 0. If/when disease worsening occurs, as evidenced by a PGA ≥ 2 , treatment will then be re-initiated and continued until a PGA of 0 is observed. Subjects entering with a PGA of 0 will have treatment discontinued and be monitored for durability of response. If/when disease worsening occurs, as evidenced by a PGA ≥ 2 , treatment will then be re-initiated and continued until a PGA of 0 is observed. This treatment and re-treatment pattern of use will be continued until the end of the study (i.e., subjects may receive study treatment up until the Week 40 visit).

Subjects who experience suspected disease worsening between scheduled study visits may contact the study site to arrange an unscheduled visit (Section 7.5). See **Disease Worsening (PGA ≥ 2) During the Study** (Section 5.1.5.2) for further instructions. Upon confirmation of disease worsening, subjects will restart treatment with study drug.

5.1.5.2. Disease Worsening (Physician Global Assessment Score ≥ 2) During the Study

If disease worsening is suspected between scheduled study visits, an unscheduled visit may be performed.

- If disease worsening (ie, PGA ≥ 2) is not confirmed, the subject will continue to be assessed at routine, scheduled visits (see Table 1).
- For each confirmed episode of disease worsening (ie, PGA ≥ 2) during the study (at either a scheduled or unscheduled visit), a treatment course of tapinarof cream (once daily) will be initiated and will continue until the subject achieves a PGA 0, as assessed at scheduled visits, approximately every 4 weeks (see Table 1).
- Subjects subsequently achieving a PGA of 0 will stop study drug and will then be assessed at routine, scheduled visits (see
- Table 1). Subjects who then experience suspected disease worsening between scheduled study visits may contact the study site to arrange an unscheduled visit (see
- Table 1).
 - If disease worsening is not confirmed, the subject will continue to be assessed at routine, scheduled visits.
 - If disease worsening is confirmed (ie, PGA ≥ 2) at either an unscheduled or a scheduled visit, subjects will initiate another treatment course of tapinarof cream (once daily) until a PGA 0 is achieved as described above.
- This treatment and re-treatment pattern of use will be continued until the end of the study (ie, subjects may receive study treatment up until the Week 40 visit).

5.1.5.3. Application of Study Drug

Study drug will be dispensed to subjects requiring treatment at the study visits specified in the Schedule of Assessments (

[Table 1](#)).

Subjects will take the tubes home and self-administer (or have a caregiver apply if necessary), except on study visit days (when study drug is applied under supervision at the site), to affected areas once daily.

Subjects will be instructed to apply study drug as follows:

- For subjects with a PGA > 0, once daily application to affected areas including those areas treated in the pivotal study; subjects are to choose the application time they prefer and to apply the study drug at that time each day of study participation.
- Subjects with a PGA of 0 will not receive treatment but if they worsen and experience a PGA of ≥ 2 , apply once daily to newly affected areas only.
- If a subject misses a daily dose, it will be recorded as a protocol deviation. The subject should continue dosing the next day and should not apply more than once daily to make up for the missed dose on the previous day.
- If chosen application time is in the evening, the dose should be applied at least 30 minutes prior to bedtime.
- Study drug should be applied to dry, clean skin
- Wash hands after application, unless treating lesions on the hands or fingernails.
- Study drug should be applied to all lesions, including newly appearing lesions and lesions that have improved during the study.
- Subjects are allowed, but not required, to treat fingernails, toenails, palms, soles, and scalp lesions with study drug; however, efficacy analyses will not include assessment of improvement of psoriasis in these areas). If using study drug on the scalp, no other treatment for scalp psoriasis is permitted during the study.
- If there is residual cream visible on the disease-affected lesional skin, then the subject should be instructed to continue to lightly rub the cream into the skin until it is no longer visible
- If study drug is applied to the subject by another person, that person should thoroughly wash his/her hands after application. When possible, use of disposable gloves is recommended.
- Subjects should record the time of study drug application in the daily diary.
- Subjects should avoid swimming, bathing, showering, or strenuous activities for at least 2 hours after application of study drug.
- On study visit days, study drug should be applied in the clinic under the supervision of site personnel and after safety assessments have been completed

NOTE: The time of the dose and assessments on study visit days will depend on the time of the study visit (either morning or afternoon visit). Therefore, the timing of the study visit may differ from the subject's chosen dosing time (morning or evening); if

this occurs, it should not be recorded as a protocol deviation and the subject should resume their chosen dosing time following any such study visit. The intention is to allow flexibility to accommodate subjects' schedules.

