Study drug will be dispensed to subjects during the study visits and will be administered at home between study visits as instructed by site personnel. Subjects will be instructed to apply study drug once daily to all affected areas, including newly appearing lesions and lesions or affected areas that improve during the study. Subjects will apply sufficient study drug to cover completely each lesion with a thin layer of study drug and will record the time of study drug application in a daily diary provided by the study site. (Note that subjects are allowed, but not required, to treat fingernails, toenails, palms, soles, and scalp lesions with study drug; however, efficacy analyses will not include assessment of improvement of psoriasis in these areas.) Subjects will be instructed to maintain the approximate dosing time chosen at the beginning of the study for their full study participation. Study drug application instructions will be reviewed at subsequent study visits. During subsequent study visits, subjects will apply the daily dose of study drug while at the study under the supervision of site personnel, after efficacy and safety

assessments have been completed. The time of the dose application and assessments will depend on the time of the study visit (either morning or afternoon visit). Therefore, the timing of the study visit may lead to a change in the subject's chosen dosing time; if this occurs, it will NOT be considered a protocol deviation; the subject should resume their chosen dosing time the day following any such clinic visit application.

Rescue medications may be initiated with consultation of the medical monitor.

Safety assessments will include AEs, local (application site) tolerability, clinical laboratory tests, vital signs, physical examinations, and investigator-assessed LTS. Efficacy assessments will include a 5-point static PGA (0-4 scale), %BSA affected, the PASI, and subject-reported DLQI.

Refer to Section 6 for descriptions of study procedures and assessments and Section 7 and the Schedule of Assessments (

[Table 1](#)) for timing of procedures and assessments.

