3. STUDY DESIGN

This is a long-term, open-label, multicenter, study to evaluate the safety and efficacy of topical tapinarof cream, 1% in adults with plaque psoriasis. Subjects in this study completed treatment with tapinarof or vehicle in 1 of 2 pivotal Phase 3 efficacy and safety studies (Study DMVT-505-3001 or Study DMVT-505-3002). The study consists of up to 40 weeks of treatment and a 4-week safety follow-up period.

At the completion of the Week-12 Visit of the pivotal study (Visit 1, Baseline [Day 1] in this study), eligibility of the subjects opting to enroll in this extension study is confirmed. Study visits during the treatment period occur every 4 weeks (± 3 days). A Phone Call is performed at Week 2 (Day 15). Unscheduled visits occur, as needed. Subjects who withdraw from the study before Week 40 return to the study center for an Early Termination Visit. The total duration of study participation is approximately 44 weeks.

At the start of the study, subjects entering with a PGA ≥ 1 receive treatment with tapinarof cream, 1% until they achieve a PGA score of 0, at which time treatment is discontinued and subjects are monitored for durability of response. If/when disease worsening occurs, as evidenced by a PGA ≥ 2 , treatment will then be re-initiated and continued until a PGA of 0 is observed.

Subjects entering with a PGA of 0 will have treatment discontinued and they will be monitored for durability of response. If/when disease worsening occurs, as evidenced by a PGA ≥ 2 , treatment is re-initiated and continued until a PGA of 0 is observed.

The pattern of treatment, suspension and re-treatment is continued until the Week 40 visit.

Study drug dispensed to subjects during the clinic visits is applied once daily to all affected areas, including newly appearing lesions and lesions that improve during the study. Subjects

apply sufficient study drug to cover completely each lesion with a thin layer of study drug and record the time of study drug application in a daily diary provided by the study site. Subjects may treat fingernails, toenails, palms, soles, and scalp lesions with study drug; however, improvement of psoriasis is not assessed in these areas.

Safety assessments include AEs, local (application site) tolerability, clinical laboratory tests, vital signs, physical examinations, and investigator-assessed LTS. Efficacy assessments include a 5-point static PGA (0-4 scale), %BSA affected, the PASI, and subject-reported DLQI.

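### Protocol 5.1.5.3 gives two different instructions on where to apply study drug when a cleared subject is re-treated

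*Protocol*

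**What the plan says.** Three bullets in Protocol 5.1.5.3 bear on where drug goes.

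- For subjects not clear: "For subjects with a PGA > 0, once daily application to affected areas including those areas treated in the pivotal study".
- For subjects who were clear: "Subjects with a PGA of 0 will not receive treatment but if they worsen and experience a PGA of" 2 or more, they are to "apply once daily to newly affected areas only".
- Further down, with no condition attached: "Study drug should be applied to all lesions, including newly appearing lesions and lesions that have improved during the study".

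Outside that list, Protocol 3.1 directs application "to all affected areas, including newly appearing lesions and lesions or affected areas that improve during the study", and the synopsis carries the same rule. SAP 3 describes drug as "applied once daily to all affected areas, including newly appearing lesions and lesions that improve during the study". None of these three places makes an exception for re-treatment.

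On when drug is re-started, Protocol 5.1.5.1 and 5.1.5.2 are uniform: treat from entry at PGA 1 or more until PGA 0, then re-start only at PGA 2 or more. If worsening at an unscheduled visit "is not confirmed, the subject will continue to be assessed at routine, scheduled visits".

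**The concern.** A subject in a re-treatment course has a PGA of at least 2, so the PGA is also above 0. On their face, all three bullets then apply to the same person on the same day. One confines treatment to newly affected areas. The other two extend it to improved lesions and to areas treated in the pivotal study. A site can follow one sentence only by departing from another.

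Repeated intermittent courses are what this study is meant to describe (Protocol 1.2 and Section 10), so the re-treatment instruction matters. If sites resolve the ambiguity differently, re-treatment courses that the SAP summarizes together will have been given under different area rules, and nothing in the listed summaries would separate them.

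**Working it through.** No sample size, error rate or event count bears on this point, so there is nothing numerical to reproduce. The check sets the instructions side by side for each state a subject can be in.

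| State | Is drug applied? | To which area? |
|---|---|---|
| (a) Enters at PGA 1 or more | Yes; all sections agree | Affected areas, including areas treated in the pivotal study; no conflict |
| (b) On treatment, improved to PGA 1 | Yes, until PGA 0; all sections agree | All lesions, including improved ones; no conflict |
| (c) Off drug after PGA 0, now PGA 1 | No, under 5.1.5.1, 5.1.5.2 and the second bullet of 5.1.5.3; only the first bullet, read alone, suggests otherwise | Does not arise if drug is not re-started |
| (d) Off drug after PGA 0, now PGA 2 or more | Yes; all sections agree | Newly affected areas only (one bullet), or all lesions including improved ones (another bullet, with an all-affected-areas rule in the synopsis, Protocol 3.1 and SAP 3) |

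The contradiction lies in state (d) and concerns area. Two situations expose it:

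1. The relapse is at a site treated before. It is affected again, but not plainly newly affected.
2. A lesion improves during the re-treatment course. One bullet keeps it under treatment because improved lesions are included. The other gives no basis for treating it unless it counts as newly affected.

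**How the area rule reaches the analysis**

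- *PGA.* Appendix 1 asks for a visual average over all treated areas at the time of the assessment. Suppose, for illustration, that a previously treated site and a new site are both active at relapse. If only the new site is treated and it clears first, an assessor who averages over the areas now under treatment could score 0 while the old site is still active. Under the all-lesions rule the old site is in the average and the score is above 0.
- *Treatment episodes.* SAP 11.7 ends an episode the day before PGA 0, so the declared date of PGA 0 sets the duration.
- *Exposure.* SAP 11.4 summarizes grams used within episodes, per expected day and per dose. A smaller treated area means fewer grams for reasons unrelated to compliance.
- *Local tolerability.* Protocol 6.3.5 and Appendix 4 ask for an average across application sites, so the set of sites is part of the score.

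The direction is not fixed. An assessor who scores overall disease, as Protocol 6.2.1.1 describes the PGA, would keep an untreated old site in the score, and the episode could then run longer.

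**The case against.** The best defence of the area wording is that PGA 0 means no signs of psoriasis (Appendix 1). Every lesion at relapse can then be called new, and the two instructions largely coincide on the day of re-start. This has real weight, and it is why one cannot say that every re-treatment course is affected. It does not cover a recurrence at a treated site, which a reasonable site may not call newly affected, or lesions that improve as the course proceeds.

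A second defence is that the bullets sort subjects by status at entry. The amendment summary in Appendix 6 describes them that way, which is evidence of intent. The current bullet does not say so: it speaks of subjects with a PGA of 0, not subjects entering with one. If the entry reading were adopted, the area treated at relapse would depend on the PGA at entry, and no other section states such a split.

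A third point is that SAP 3 summarizes the design and does not instruct sites. That is fair. It adds little to the conflict at site level and shows mainly that the analysis plan carries no re-treatment exception.

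A reader might also infer a second contradiction, in which the first bullet has subjects apply drug at any PGA above 0 while other sections re-start only at 2 or more. The documents do not support this. On a 0 to 4 scale, PGA above 0 is the entry rule of PGA 1 or more. The re-start rule of PGA 2 or more is given in Protocol 3.1, 5.1.5.1 and 5.1.5.2 and in SAP 3, and the next bullet of 5.1.5.3 repeats it. Section 5.1.5.2 gives no re-start when worsening is not confirmed, and 5.1.5.3 opens by addressing subjects who require treatment. What remains is a loosely scoped bullet that does not say whether it means subjects entering or subjects on treatment.

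**Conclusion.** Wrong as written, on area only. For a subject cleared to PGA 0 who worsens to PGA 2 or more, Protocol 5.1.5.3 contains two incompatible instructions on where to apply drug, and the synopsis, Protocol 3.1 and SAP 3 do not resolve them.

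The outputs exposed are the date of PGA 0 within a re-treatment course, treatment-episode duration, grams used and local tolerability averages. The size of the effect is unknown: the documents do not say how often relapse occurs at treated sites or how sites read the bullet. The effect on the PGA also assumes that assessors follow Appendix 1 and average over treated areas.

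A reader might go further and infer that off-drug time is contaminated by dosing at PGA 1, shifting time to worsening by one or more 4-week visit intervals. That rests on the threshold reading, which does not hold, and no calculation in the documents supports such a shift. For the same reason, the point does not call for a SAP flag on doses between clearance and relapse, or for a durability analysis with and without those subjects.

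**What to change.** Reconcile the bullets in Protocol 5.1.5.3 with each other and with the synopsis, Protocol 3.1 and SAP 3, so that a single area rule for re-treatment appears throughout. The wording should settle both exposed situations: recurrence at a previously treated site, and a lesion that improves during the course. Which rule to adopt is a clinical decision for the sponsor, and none is proposed here.

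In the same edit, state whom the PGA > 0 bullet covers, so that it matches 5.1.5.1 and 5.1.5.2 on its face.

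The cost is a short protocol clarification with the usual ethics and regulatory submission, a note to sites, and a matching check of the sentence in SAP 3. No new data or analysis is needed. The edit helps only courses given after it reaches the sites.

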5.2. Randomization/Treatment Assignment

All subjects will receive treatment with tapinarof cream, 1% as needed per protocol.

5.3. Blinding

This study is an open-label study; blinding is not applicable.

5.4. Compliance with Study Drug Administration

At baseline, study staff will provide the subject with detailed instructions concerning protocol requirements and use of study drug in this extension study. Additionally, subjects will be asked to complete a daily diary with the time of each application of study drug. At each postbaseline study visit, study staff will review use of study drug, as applicable, with the subject.

When subjects are dosed at the site, they will apply the study drug under supervision of the study staff. The date and time of each dose administered in the clinic will be recorded in the source documents. The study drug and study subject identification will be confirmed at the time of dosing by a member of the study site staff.

At the time of dispensing study drug to each subject, site personnel will weigh the tubes to be dispensed and will record the weight of all tubes dispensed at each visit in the drug accountability logs. Subjects will be instructed to bring all used and unused tubes with them to each study visit. Site personnel will weigh the returned tubes (used and unused) and record the weight in the drug accountability logs. If a tube has been lost, discarded, or forgotten by the subject, the site personnel will make a notation of this on the drug accountability logs. The site personnel will remind the subject to keep all tubes of study drug dispensed and to bring all used and unused tubes to each study visit. These data will be used to estimate subject compliance with use of study drug. Tubes of study medication dispensed at the most recent prior visit, which remain unopened (the foil cap on the tube remains fully intact/undisturbed) may be redispensed to study subjects at the current visit. Unopened tubes may only be dispensed one time. Opened, partially used tubes, or tubes with foil overlay removed are not to be redispensed to study subjects. If there is any question as to redispensation, sites should issue new tubes of study medication to the subject(s).

5.5. Treatment after the End of the Study

Subjects will not receive any additional treatment with the study drug from the Sponsor after completion of the study. The indication being studied is not life threatening or seriously debilitating, and other treatment options are available.

The Investigator is responsible for ensuring that consideration has been given to the poststudy care of the subject's medical condition, whether or not the Sponsor is providing specific poststudy drug.

5.6. Prior and Concomitant Therapy

The Medical Monitor should be contacted if there are any questions regarding concomitant or prior therapy.

5.6.1. Permitted Medications and Nondrug Therapies

Concomitant medications for medical treatment of other conditions are allowed, under the condition that the dosage and administration of these treatments is not planned to change from the Baseline visit to the completion of the study or discontinuation, and that the medication is not a prohibited medication as described in Section 5.6.2. In the event of skin infection, topical antibacterial agents can be applied to the infected area; however, study drug must not be applied to the area until the skin infection is healed.

Subjects may use nonmedicated shampoos (must not contain corticosteroids, vitamin D analogs, salicylic acid, or coal tar). Nonmedicated emollients may be used on nonlesional skin; emollients should not be applied to lesional skin during active treatment courses and should not be applied on the morning of study visits. The same emollient should be used throughout the subject's participation in the study.

Note: Any emollient used during the study must be recorded as a concomitant medication.

